## **1. AMENDMENTS FROM PREVIOUS VERSION(S)**

This document is the original version from February 28, 2020.

## **2. INTRODUCTION**

*PF-07059013 is a novel small molecule allosteric modulator of hemoglobin that is currently being developed for the treatment of Sickle Cell Disease.*

*The purpose of the study is to evaluate the safety, tolerability, pharmacokinetics (PK) and pharmacodynamic (PD) of single and multiple ascending oral doses of PF-07059013 in healthy adult participants. Additionally, effects of different formulations and food on parameters, including PK, after single oral dose, may be explored. This study is the first time that PF-07059013 will be administered to humans, and the results obtained from this study will inform future clinical development of PF-07059013.*

### **2.1. Study Design**

*This study consists of 3 parts, with ongoing review of safety, tolerability, PK and PD data planned.*

*Part 1 comprises of 4 periods with 2 interleaving cohorts of healthy adult participants. Part 1 Period 1 to 3 is investigator- and participant-blinded, sponsor-open, randomized, single ascending dose, with 3-period placebo substitution crossover, and Period 4 will be open-label.*

*Part 2 of this study will be investigator- and participant-blinded, sponsor-open, randomized, placebo-controlled, sequential, multiple ascending dose, with 3 planned cohorts of healthy adult participants. Two additional cohorts of healthy adult participants may be included to permit assessment of any of the following: repeat of a previously administered dose level; studying additional dose levels as dictated by the evaluated safety, tolerability or PK of earlier dose levels; or any other assessment needed to meet the objectives of this study.*

*Part 3 of this study will be an open label, randomized, 4-period crossover, single dose assessment of formulation and/or food effects in healthy adult participants.*

Block randomization will be used to protect against possible temporal enrollment or dropout effects. In Part 1 with the 3-period crossover and no randomization for period 4, the block size of 3 (2:1 active to placebo ratio) will be used for each cohort (N=9). In Part 2 the block size of 4 (3:1 active to placebo ratio) will be used for each cohort (N=8). In Part 3 cohort (N=12) with the 4-period crossover, the block size of 4 will be used.

*For all parts of the study, participants will be screened within 28 days of their first dose of investigational product. Participants will be admitted to the CRU on Day -1 and may be discharged at investigator discretion following completion of assessments per Schedule of Activities.*

*In Part 1 each participant may receive up to 3 single oral doses of PF-07059013 suspension and up to 1 placebo dose. For Period 1 to 3, at each period, approximately 6 participants will receive a single dose of PF-07059013 suspension formulated with polymer, and approximately 3 participants will receive placebo formulated with polymer. In Period 4, a single dose of PF-07059013 suspension, formulated without polymer, will be administered at a dose level that has been previously administered in the same cohort. Between each dose administration to a given participant there will be a washout interval of at least 14 days.*

*In Part 2 each participant may receive multiple oral doses of PF-07059013 suspension (either with or without polymer, depending on results from Part 1) or placebo, over a duration of 14 days, depending on randomization.*

*In Part 3 each participant may receive single oral dose of suspension with different formulations, or tablet, either under fasted condition or following a high fat/high caloric meal. Between each dose administration to a given participant there will be a washout interval of at least 14 days.*

[figure not shown]
[figure not shown]
[figure not shown]
*Participants who discontinue for non-safety related reasons prior to completion of the study may be replaced, at the discretion of the principal investigator (PI) and sponsor. The replacement participant(s) may or may not be required to complete all Periods of the cohort in which they are participating at the discretion of the PI and sponsor.*

*A participant is considered to have completed the study if he/she has completed all phases of the study, including the last scheduled procedure shown in the Schedule of Activities and any requested unplanned visits.*

*The end of the study is defined as the date of the last scheduled procedure shown in the Schedule of Activities for the last participant in the trial.*

*A schematic of the overall study design is provided in Figure 1.*

**Figure 1. Sample Study Schematic**

The table below presents the Part 3 randomization sequences.

Cohort	n	Period 1	Period 2	Period 3	Period 4
N=12	n=3	A	B	C	D
	n=3	A	B	D	C
	n=3	B	A	C	D
	n=3	B	A	D	C

Treatment A: PF-07059013 oral suspension (Small particle size), fasted, with Polyvinylpyrrolidone (PVP).

Treatment B: PF-07059013 oral tablet, fasted, without PVP.

Treatment C: PF-07059013 oral suspension (Small particle size), fed, with PVP.

Treatment D: PF-07059013 oral suspension (Moderate particle size), fasted, with PVP.

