1.2. Schema

Sample study design schematics of Study Part 1, 2 and 3 are provided below. Doses are provided for illustrative purpose only.

Sample Dosing Scheme (Part 3 – Formulation and Food Effect)

Cohort		Period 1	Period 2	Period 3	Period 4
8	N=2	A	B	C	D
	N=2	D	A	B	C
	N=2	C	D	A	B
	N=2	B	C	D	A

Treatment A: PF-07059013 oral suspension (Small particle size), fasted.

Treatment B: PF-07059013 oral suspension (Small particle size), fed.

Treatment C: PF-07059013 oral suspension (Moderate particle size), fasted.

Treatment D: PF-07059013 oral tablet, fasted.

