The statistical comparison of PF-07059013 PK parameters following high-fat/high-caloric meal (Test) versus overnight fast (Reference), moderate particle size (Test) versus small particle size (Reference) suspension administered under fasted condition, and tablet formulation (Test) versus small particle size suspension formulation (Reference) administered under fasted condition will be detailed in the SAP. The analyses will include reporting the ratio of adjusted geometric means (Test/Reference) and 90% confidence intervals for the ratios for C_{max} , **CCI** as data permit.

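### The SAP's Part 3 sequences put the reference only in Periods 1–2 and the fed and moderate-particle treatments only in Periods 3–4, so food and particle-size effects cannot be separated from period

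*SAP*

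**What the plan says.** Under Figure 1, the SAP introduces a table with the words "The table below presents the Part 3 randomization sequences". The rows are ABCD, ABDC, BACD and BADC, each with n=3. SAP section 2.1 agrees on size: "In Part 3 cohort (N=12) with the 4-period crossover, the block size of 4 will be used".

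In the SAP's labels, A is the small-particle suspension given fasted with PVP, B is the tablet taken fasted without PVP, and D is the moderate-particle suspension given fasted with PVP. The food-effect arm is defined as "Treatment C: PF-07059013 oral suspension (Small particle size), fed, with PVP".

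Protocol section 9.4.2.2 names three comparisons: high-fat meal against fasting, moderate against small particle size, and tablet against small-particle suspension. It commits to estimates: "The analyses will include reporting the ratio of adjusted geometric means (Test/Reference) and 90% confidence intervals for the ratios". In SAP labels these are C/A, D/A and B/A.

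Protocol section 1.2 shows a sample Part 3 scheme with rows ABCD, DABC, CDAB and BCDA, in which every treatment appears in every period. The letters differ there (B is the fed suspension, C the moderate particle size, D the tablet), so comparisons between the two documents must be matched by description. Protocol section 4.1 allows treatment sequences to be adjusted on emerging safety, tolerability and PK data. The readable SAP text gives no reason for the new layout and does not mention its effect on the comparisons.

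**The concern.** A crossover removes period effects by giving each treatment in different periods to different participants. The SAP's four sequences do this only within two blocks. A and B swap places in Periods 1–2, and C and D swap places in Periods 3–4, but no participant receives C or D early or A or B late. The food and particle-size comparisons both run across the blocks, so each is a late-period treatment set against an early-period reference in every participant.

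That affects two of the three questions Part 3 was set up to explore. Protocol section 4.2 says the food result is to help choose the dose and the fed or fasted condition for later studies, and that the formulation results are to guide development. A ratio that contains an unknown period shift, with an interval that takes no account of it, is a poor basis for those choices.

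**Working it through.** **Inputs.** The sequences, n=3 per row and N=12 come from SAP Figure 1 and section 2.1. The comparisons come from protocol section 9.4.2.2, and the comparator scheme from protocol section 1.2. The plan's own figure reproduces: 4 sequences × 3 = 12. There is no power figure to reproduce, since protocol section 9.2 states that no formal sample size calculation was made.

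**Step 1: participants per period under the SAP.**

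| Treatment | P1 | P2 | P3 | P4 |
|---|---|---|---|---|
| A, reference | 6 | 6 | 0 | 0 |
| B, tablet | 6 | 6 | 0 | 0 |
| C, fed | 0 | 0 | 6 | 6 |
| D, moderate particle | 0 | 0 | 6 | 6 |

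The indicator for Period 3 or 4 is identical to the indicator for treatment C or D.

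**Step 2: estimability.** Take log exposure = participant + period + treatment + error. There are 12 participant, 3 period and 3 treatment columns, 18 in all.

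| Sequences (N=12) | Rank | Food | Particle size | Tablet |
|---|---|---|---|---|
| SAP | 17 of 18 | not estimable | not estimable | 0.167σ² |
| Protocol Latin square | 18 of 18 | 0.167σ² | 0.167σ² | 0.167σ² |
| Williams square | 18 of 18 | 0.167σ² | 0.167σ² | 0.167σ² |

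Here σ² is the within-participant variance on the log scale, and 0.167σ² = 2σ²/12. At the protocol's N=8 the Latin square also has full rank (14 of 14), with variance 2σ²/8 = 0.25σ². Under the SAP, D−C is estimable too, but it is not a planned comparison.

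Treating participants as random does not help: the fixed part has rank 6 of 7. Every participant follows the same block order, so between-participant information cannot separate the effects either.

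**Step 3: if period is left out.** All contrasts can then be computed. Suppose there is no true treatment effect and Periods 3–4 sit δ above Periods 1–2 on the log scale. The expected C−A and D−A are then both δ, and B−A is 0. Under the protocol's scheme the same shift gives 0 for the food comparison.

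For interval coverage, assume a within-participant CV of 30%. Then σ = √ln(1 + 0.30²) = 0.294, and the standard error is 0.294 × √(2/12) = 0.120. Coverage follows from the noncentral t distribution with noncentrality δ/0.120. The pooled model without period has 48 − 15 = 33 error degrees of freedom; a paired analysis has 11.

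| δ (assumed) | Expected ratio e^δ | Coverage of nominal 90% CI, 33 df | 11 df |
|---|---|---|---|
| 0 | 1.00 | 90% | 90% |
| 0.05 | 1.05 | 87% | 87% |
| 0.10 | 1.11 | 79% | 80% |
| 0.20 | 1.22 | 50% | 53% |

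**Step 4: a side effect on adverse events.** SAP section 6.2.1 attributes events in washout and follow-up to the preceding treatment. With 14-day washouts and follow-up contact 28 to 35 days after the last dose, A and B each carry 14 days. C and D carry on average (14 + 28)/2 = 21 to (14 + 35)/2 = 24.5 days.

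**The case against.** The best case on the other side concerns the stakes. Part 3 serves none of the readable primary or secondary objectives, which cover Parts 1 and 2. It is optional and called preliminary, no hypothesis is tested, and SAP section 8.2.1 calls the main Part 3 analyses descriptive. The protocol's scheme is labelled a sample, and sequences may be adjusted. Figure 1 is also titled a sample schematic. Fixed order is accepted elsewhere: the polymer-free suspension is always given in Period 4 of Part 1. A reason or caveat may sit in blacked-out text. No document gives a size for any period effect.

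Much of this stands as a limit on importance. No formal test fails, and neither the safety objective nor dose escalation depends on Part 3. The shifts and the CV are assumptions. Residual drug is an unlikely source of drift: the planned 14-day washout is 336/41 ≈ 8.2 of the longest predicted half-life (41 hours at 3000 mg), leaving about 0.3%. The aliasing is with one contrast, Periods 3–4 against 1–2, and not with every period difference.

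None of it makes the two comparisons estimable. Permission to change sequences does not supply the missing information, and a blacked-out rationale could explain the layout but not repair it. The sentence above the table presents these as the randomization sequences, and they match the stated N and block size. A descriptive ratio with a 90% interval will still be read as a treatment effect. The data cannot show whether the period shift is small, because that shift is itself not estimable.

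**Conclusion.** The concern holds. Under the SAP's sequences, the food (C/A) and particle-size (D/A) ratios cannot be separated from the difference between Periods 3–4 and Periods 1–2. Only the tablet comparison (B/A) is free of period. This is exact and depends on no assumption about variability or about the unreadable Part 3 model. If that model includes period, the two ratios do not exist; if it omits period, they carry the whole shift.

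The size of the resulting bias is unknown. The coverage loss, from 90% to about 79% at a shift of 0.10 and 50–53% at 0.20, illustrates it under an assumed 30% CV. Part 3 is exploratory, but this takes away its ability to answer two of its own three questions, which the protocol's scheme could answer with the same number of participants.

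**What to change.** Replace the four sequences with a 4×4 Williams square at n=3 per sequence. In SAP labels, ABDC, BCAD, CDBA and DACB would serve: each treatment appears once in every period, and each of the 12 ordered pairs of successive treatments occurs once. The protocol's Latin square is the minimum; it restores estimability but does not balance which treatment precedes which. State the model in the SAP with sequence, period and treatment as fixed effects and participant as random. Use one set of treatment letters in both documents.

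If the list has already been used, report B/A as the only planned comparison free of period. Label C/A and D/A as confounded with the change from Periods 1–2 to Periods 3–4.

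The cost is a reissued Part 3 randomization list and one SAP table. Participants, visits and samples stay the same. The practical drawback is that all four treatments, including the tablet and the high-fat meal, must be ready at Period 1. If supply is the reason for the present layout, the SAP should say so and carry the label above.

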## 2.2. Study Objectives

### 2.2.1. Primary Objectives

In Part 1 and 2: *To evaluate safety and tolerability of single and multiple escalating oral doses of PF-07059013 suspension administered in healthy adult participants.*

### 2.2.2. Secondary Objectives

In Part 1 and 2: *To characterize the blood and plasma exposures of PF-07059013 following administration of single and multiple oral suspension doses in healthy adult participants.*

In Part 1 and 2: *To evaluate the PD profile of PF-07059013 following administration of single and multiple oral doses of suspension in healthy adult participants.*

CCI

### 3. INTERIM ANALYSES, FINAL ANALYSES AND UNBLINDING

*No formal interim analysis will be conducted for this study. Safety, pharmacokinetic (PK) and pharmacodynamic (PD) data will be reviewed after each cohort.*

This is a sponsor open study, with the investigators and participants blinded to study treatment (with exception of Part 1 period 4 and Part 3). Specific Pfizer personnel (e.g.

analytical staff, medical monitor, clinician, statistician, and clinical pharmacologist) will be unblinded to subject treatments in order to permit real-time interpretation of the safety and PK/PD data, and to provide information necessary to potentially alter the dose escalation sequence. To minimize the potential for bias, treatment randomization information will be kept confidential by Pfizer personnel and will not be released to the investigator/study staff until the conclusion of the study. Unblinding will not be performed until the final database has been locked for all cohorts. Final analysis will follow the official database release.

#### 4. HYPOTHESES AND DECISION RULES

CCI

[figure not shown]
CCI

CCI

• CCI

## 5. ANALYSIS SETS

### 5.1 Full Analysis Set

Not applicable. Analysis sets for PK, PD, safety **CCI** [REDACTED] data are defined in Sections 5.2, 5.3, 5.4 and 5.5.

### 5.2 Pharmacokinetic Analysis Set

#### 5.2.1 Concentration Analysis Set

*The PK concentration population will be defined as all randomized participants who received at least 1 dose of PF-07059013 and in whom at least 1 plasma and blood concentration value is reported.*

#### 5.2.2 Parameter Analysis Set

*The PK parameter analysis population will be defined as all randomized participants who received at least 1 dose of PF-07059013 and who have at least 1 of the PK parameters of interest calculated.*

### 5.3 Pharmacodynamic Analysis Set

*The PD analysis population is defined as all randomized participants who received at least one dose and have at least one PD assessment in at least one cohort.*

### 5.4 Safety Analysis Set

*All participants randomly assigned to study intervention and who take at least 1 dose of study intervention. Participants will be analyzed according to the product they actually received.*

**CC** [REDACTED]

**I**

[REDACTED]

[REDACTED]

### 5.6 Treatment Misallocations

All analyses will be performed on an “as-treated” basis and will not include data from participants who are randomized but not treated.

If a participant takes a treatment that is not consistent with the treatment they are randomized to then they will be reported under the treatment that they actually receive for all safety, PK **CCI** [REDACTED], where applicable.

### 5.7 Protocol Deviations

Participants who experience events that may affect their PK/PD profile (eg dosing error, etc) may be excluded from the PK/PD analysis. At the discretion of the pharmacokineticist a concentration value may also be excluded if the deviation in sampling time is of sufficient concern or if the concentration is anomalous for any other reason.

A full list of protocol deviations will be compiled and reviewed to identify major and minor deviations prior to database closure.

### **5.7.1 Deviations Assessed Prior to Randomization**

At screening, the investigator will assess participants against the inclusion and exclusion criteria as set out in Sections 5.1 and 5.2 of the protocol.

### **5.7.2 Deviations Assessed Post-Randomization**

Any significant deviation from the protocol will be reviewed prior to database closure and a decision taken regarding evaluation for each analysis population.

## **6. ENDPOINTS AND COVARIATES**

### **6.1. Efficacy Endpoint(s)**

None.

### **6.2. Safety Endpoints**

In this section, the safety endpoints that will be measured during the study are detailed. Where applicable, details of the endpoints to be derived and definition of baseline are also provided.

The following data are considered in standard safety summaries (see protocol for collection days and list of parameters):

- adverse events,
- clinical laboratory data,
- vital signs data,
- ECG and telemetry results.

#### **6.2.1. Adverse Events**

Any events occurring following start of treatment or increasing in severity will be counted as treatment emergent.

Events that occur in a non-treatment period subsequent to dosing (for example, washout or follow-up) will be counted as treatment emergent and attributed to the previous treatment taken.

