Each participant may receive up to 3 single oral doses of PF-07059013 suspension and up to 1 placebo dose. For Period 1 to 3, at each period, approximately 6 participants will receive a single dose of PF-07059013 suspension formulated with polymer, and approximately 3 participants will receive placebo. In Period 4, a single dose of PF-07059013 suspension, formulated without polymer, will be administered at a dose level that has been previously administered in the same cohort. Between each dose administration to a given participant there will be a washout interval of at least 14 days. The washout interval may be adjusted based on data emerging from previous cohorts/periods. An on-site visit is scheduled for Day 8 (± 1 day) of Period 3 and 4, and telephone follow-up contact will occur 28 to 35 days after the last dose of investigational product in the final period. The total planned duration of participation, from the Screening visit to the Follow-up phone call, is approximately 15 weeks.

Part 2 – Multiple Ascending Dose

Each participant may receive multiple oral doses of PF-07059013 suspension (either with or without polymer, depending on results from Part 1) or placebo, over a duration of 14 days, depending on randomization. Participants will be required to stay at the CRU for the duration of the treatment phase. An on-site follow-up visit and a telephone follow-up contact will take place at Day 21 (± 1 day) and between Day 42-49, respectively. The total planned duration of participation, from the Screening visit to the Follow-up phone call, is approximately 10 weeks.

Part 3 – Formulation and Food Effects

Each participant may receive single oral dose of suspension with different formulations, or tablet, either under fasted condition or following a high-fat/high-caloric meal. Between each dose administration to a given participant there will be a washout interval of at least 14 days. The washout interval may be adjusted based on data emerging from previous cohorts/periods. A telephone follow-up contact will occur 28 to 35 days after the last dose of investigational product in the final period. The total planned duration of participation, from the Screening visit to the Follow-up phone call, is approximately 15 weeks.

Data Monitoring Committee or Other Independent Oversight Committee: No

[figure not shown]
[figure not shown]
[figure not shown]
Statistical Methods

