Abbreviations: → = ongoing/continuous event; aPTT = activated partial thromboplastin time; E/T = early termination; F/U = follow-up; HBcAb = hepatitis B core antibody; HBcAg = hepatitis B core antigen; HBsAg = hepatitis B surface antigen; HCVAb = hepatitis C antibody; HIV = human immunodeficiency virus; CRU = clinical research unit; ECG = electrocardiogram; FSH = follicle-stimulating hormone; H= hour; p20 = oxygen pressure at which 20% of the hemoglobin in a given blood sample is oxygenated; p50 = oxygen pressure at which 50% of the hemoglobin in a given blood sample is oxygenated; PT/INR = prothrombin time/internationalized normalized ratio.

A. Part 1 SoA – Single Ascending Dose

Visit Identifier ^a	Screening	Period 1 to Period 4 ^b											F/U Contact ^c	E/T	
Days Relative to Day 1	Day -28 to Day -2	Day -1	Day 1					Day 2		Day 3	Day 4	Day 5	Visit ^d Day 8±1	28-35 Days	
Hours Post dose			0 ^e	0.5	1	2	5	8	12	24	36	48	72	96	168

- a. **Visit Identifier:** Day relative to start of study treatment (Day 1).
- b. **Period 1 to Period 4:** Washout duration of at least 14 days between periods. May be adjusted based on emerging data.
- c. **F/U Contact:** Follow-up phone call may occur via telephone and must occur 28 to 35 days after the last dose of investigational product in the final period.
- d. **Visit Day 8:** Only applicable for Period 3 and 4.
- e. **Day 1 0 H:** Predose sample collection/procedure, except for study treatment administration.
- f. **Physical Examination:** Complete physical examination will be conducted at Screening or upon admission (Day -1) in Period 1. Brief physical examination may be performed at other times, as appropriate, for findings during previous examination or new/open AEs, at investigator's discretion.
- g. **12-lead ECG:** Single at Screening, and triplicate at all other timepoints.
- h. **Supine blood pressure:** Where orthostatic blood pressure assessment will be conducted, supine blood pressure does not need to be repeated separately.
- i. **Continuous cardiac telemetry monitoring:** Baseline telemetry to be recorded for at least 2 hours between admission and prior to dosing in Period 1 only while awake. Post dose telemetry will continue for 12 hours after dosing for each period.
- j. **Study Treatment Administration:** Participants should fast for at least 10 hours prior to dosing. Refer to [Section 6.1.1](#) and [Section 5.3.1](#).

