4. STUDY DESIGN

4.1. Overall Design

This study consists of 3 parts, with ongoing review of safety, tolerability, PK and PD data planned.

Part 1 – Single Ascending Dose

The design for Period 1 to 3 for Part 1 of this study is investigator- and participant-blinded, sponsor-open, randomized, single ascending dose, with 3-period placebo substitution crossover, while Period 4 will be open-label. There will be 2 interleaving cohorts of healthy adult participants, with a total of approximately 18 participants planned (approximately 9 participants in each cohort). Each participant may receive up to 3 single oral doses of PF-07059013 and up to 1 placebo dose. For Period 1 to 3, at each period, approximately 6 participants will receive a single dose of PF-07059013 oral suspension formulated with polymer, and approximately 3 participants will receive placebo. In Period 4, a single dose of PF-07059013 oral suspension, formulated without polymer, will be administered at a dose level that has been previously administered in the same cohort.

Part 2 – Multiple Ascending Dose

Part 2 of this study will be investigator- and participant-blinded, sponsor-open, randomized, placebo-controlled, sequential, multiple ascending dose. A total of approximately 24 healthy adult participants will be randomized for Cohort 3 to 5. In each cohort, approximately 6 participants will receive PF-07059013 oral suspension (either with or without polymer, depending on results from Part 1) and approximately 2 participants will receive placebo, over a duration of 14 days, depending on randomization. Two additional cohorts (optional Cohort 6 and 7) with approximately 8 participants each, with the same randomization ratio may be included to permit assessment of any of the following: repeat of a previously administered dose level; studying additional dose levels as dictated by the evaluated safety, tolerability or PK of earlier dose levels; or any other assessment needed to meet the objectives of this study.

The first dose level in Part 2 will only initiate after review of safety and PK data from both cohorts in Part 1 Period 4. Refer to [Section 4.3.3](#) for additional details regarding determination of initial dose in Part 2 relative to dose(s) evaluated in Part 1.

Part 3 – Formulation and Food Effects

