8.3.1. Time Period and Frequency for Collecting AE and SAE Information

The time period for actively eliciting and collecting AEs and SAEs (“active collection period”) for each participant begins from the time the participant provides informed consent, which is obtained before the participant’s participation in the study (ie, before undergoing any study-related procedure and/or receiving study intervention), through and including a minimum of 28 calendar days, except as indicated below, after the last administration of the study intervention.

Follow-up by the investigator continues throughout and after the active collection period and until the AE or SAE or its sequelae resolve or stabilize at a level acceptable to the investigator and Pfizer concurs with that assessment.

For participants who are screen failures, the active collection period ends when screen failure status is determined.

If the participant withdraws from the study and also withdraws consent for the collection of future information, the active collection period ends when consent is withdrawn.

If a participant definitively discontinues or temporarily discontinues study intervention because of an AE or SAE, the AE or SAE must be recorded on the CRF and the SAE reported using the CT SAE Report Form.

Investigators are not obligated to actively seek AE or SAE after the participant has concluded study participation. However, if the investigator learns of any SAE, including a death, at any time after a participant has completed the study, and he/she considers the event to be reasonably related to the study intervention, the investigator must promptly report the SAE to Pfizer using the CT SAE Report Form.

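### In Part 1 the AE attribution rule gives the Period 4 treatment a 28-35 day window against about 14 days for placebo and the with-polymer doses, so its AE column is not comparable with theirs

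*SAP*

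**What the plan says.** SAP 6.2.1 counts any event in a non-treatment period after dosing, such as washout or follow-up, as treatment emergent: it "will be counted as treatment emergent and attributed to the previous treatment taken". No lag or maximum number of days is given. SAP 8.3 calls for safety summaries split by treatment, with each Part handled separately. SAP 8.3.4 adds only that AEs follow the sponsor's reporting standards. Neither document states a common window or an exposure-adjusted rate.

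The time available after each dose depends on the period:

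- **Periods 1-3.** SAP 2.1: "Between each dose administration to a given participant there will be a washout interval of at least 14 days". The protocol's Part 1 schedule (section 1.3) adds flexibility: "Washout duration of at least 14 days between periods. May be adjusted based on emerging data".
- **Final period.** Protocol synopsis: "telephone follow-up contact will occur 28 to 35 days after the last dose of investigational product in the final period". Protocol 8.3.1 requires active AE collection "through and including a minimum of 28 calendar days, except as indicated below, after the last administration of the study intervention".
- **Who receives what.** Protocol 4.1 describes Periods 1-3 as blinded, "with 3-period placebo substitution crossover, while Period 4 will be open-label". In each of Periods 1-3 about 6 participants per cohort receive drug with polymer and "approximately 3 participants will receive placebo". Period 4 is active drug without polymer for everyone.

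**The concern.** Because Period 4 always comes last, its AE window is longer by design than that of any other planned Part 1 treatment. A table of the percentage of participants with an AE would then show more events under the without-polymer suspension even if the drug did nothing. Period 4 has no concurrent placebo group in which the same rise would appear.

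AEs are part of the primary endpoint for Parts 1 and 2. Period 4 is there to guide formulation development, the choice of suspension for Part 2 depends on Part 1 results, and Part 2 starts only after safety and PK data from Period 4 have been reviewed. A reader comparing formulations on tolerability would be comparing windows of different length.

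**Working it through.** **1. Is 14 days the right planning figure?** The stated Part 1 participation is about 15 weeks. Inputs: screening up to 28 days, three washouts of at least 14 days, follow-up at 28-35 days.

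- 28 + 3 × 14 + 28 = 98 days = 14.0 weeks
- 28 + 3 × 14 + 35 = 105 days = 15.0 weeks

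This reproduces the stated figure. Washouts of 21 days would give 17-18 weeks. If 105 days is taken as exact and screening uses all 28 days, the average washout is at most (105 − 28 − 28)/3 = 16.3 days, or (105 − 28 − 35)/3 = 14.0 days.

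**2. Windows in Part 1.** Placebo doses: 3 per period × 3 periods × 2 cohorts = 18. Period 4 doses: 9 × 2 = 18.

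| Treatment | Days per dose | Participant-days |
|---|---|---|
| Placebo (Periods 1-3) | 14 | 18 × 14 = 252 |
| Without polymer (Period 4) | 28-35 | 18 × 28 = 504 to 18 × 35 = 630 |

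The ratio is 28/14 = 2.0 to 35/14 = 2.5. It falls to 1.75-2.2 with 16-day washouts and 1.3-1.7 with 21-day washouts. The with-polymer doses have the same per-dose window as placebo.

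**3. Effect on incidence with no drug effect.** The documents give no background AE rate, so the 14-day incidence p is an assumption. Incidence over d days is 1 − (1 − p)^k, where k is the cumulative hazard to day d divided by that to day 14.

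- *Constant hazard:* k = d/14, so k = 2.0 or 2.5.
  - p = 5% gives 9.8-12.0%.
  - p = 10% gives 19.0-23.2%.
  - p = 20% gives 1 − 0.8^2 = 36.0% to 1 − 0.8^2.5 = 42.8%.
- *Early clustering:* assume 80% of the 14-day hazard falls in the first 4 days and the other 20% is spread evenly over the next 10, continuing at that rate. Then k = 1 + 0.2 × 14/10 = 1.28 at 28 days and 1 + 0.2 × 21/10 = 1.42 at 35 days.
  - p = 20% gives 1 − 0.8^1.28 = 24.8% to 1 − 0.8^1.42 = 27.2%.

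At p = 20%, the expected number of 18 participants with an AE is 3.6 on placebo. In Period 4 it is 4.5-4.9 with early clustering and 6.5-7.7 with a constant hazard.

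**4. Part 3.** The SAP's four sequences (n = 3 each) all start with A and B in Periods 1-2 and finish with C and D in either order. A and B are never last; C and D are each last in 6 of 12 participants.

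- A and B: 14 days
- C and D: (6 × 14 + 6 × 28)/12 = 21 days to (6 × 14 + 6 × 35)/12 = 24.5 days

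Treatment A, the fasted small-particle suspension used as reference, therefore never has the long window. Under the protocol's illustrative Part 3 scheme (section 1.2), each treatment is last equally often and the imbalance does not arise.

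**The case against.** A reader might infer that the Part 1 and Part 2 AE tables as a whole are not like for like. The documents do not support that. Active and placebo in Periods 1-3 share the same planned washout, and Part 2 has parallel arms with the same follow-up. These are the placebo-controlled comparisons, and they stand.

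A reader might also take 36-43% as the expected distortion. That needs a constant hazard. Participants are confined and closely monitored up to Day 5, and after the Day 8 visit in Period 4 the only scheduled contact is a telephone call. The longest projected effective half-life is 41 hours, so five half-lives take 5 × 41 = 205 hours, about 8.5 days. Clustering of events soon after dosing is plausible, so the constant-hazard figures are an upper illustration.

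Other points carry weight:

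- Period 4 is open-label, not randomised, always last and without placebo, and only Periods 3 and 4 have the Day 8 visit. Equal windows would not remove those differences.
- Safety analysis is descriptive, and listings are ordered by study day within treatment period, so late events can be found. Part 1 escalation uses safety data to a minimum of 72 hours and does not depend on this rule.
- Counting late events under active drug errs towards over-reporting, which is defensible in a first-in-human study. Taking them out of the main table would be debatable.
- The sponsor's reporting standards are not among the documents and might contain a lag rule. But the SAP states its own rule without one, so possible wording elsewhere does not settle the matter.
- Part 3 is outside the primary objective, so the case there is one of consistency between treatments.

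**Conclusion.** The point holds for the Period 4 column of the Part 1 by-treatment AE table, and for C and D against A and B under the SAP's Part 3 sequences. The planned Part 1 window is 2.0-2.5 times longer for Period 4, assuming washouts near the 14-day minimum, which the 15-week duration supports. With no drug effect and an assumed 20% incidence in 14 days, Period 4 would show about 25-27% with early clustering and up to 36-43% with a constant hazard: roughly 1 to 4 extra participants of 18.

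The consequence is for descriptive interpretation. No hypothesis is tested, so no error rate is affected. It also does not follow that any observed excess in Period 4 must be an artefact; the present layout simply could not separate window length from a formulation effect.

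**What to change.** In SAP 6.2.1 and 8.3.4:

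1. Keep the all-events treatment-emergent table and the present attribution rule, so that no event leaves the main record.
2. For Parts 1 and 3, add a by-treatment AE table limited to onset from dosing to the earlier of the next dose or 14 days. In Part 1 this gives 18 × 14 = 252 participant-days for both placebo and Period 4.
3. State that any comparison between treatments uses the common-window table.
4. Footnote the all-events table to say that follow-up is 28-35 days after the final-period dose and about 14 days after earlier doses, giving the actual intervals.

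The cost is some SAP wording and one extra table for each of the two Parts. Data collection is unchanged. The limit of the fix is that equal windows do not make Period 4 randomised, blinded or placebo-controlled, and the text accompanying the table should say so.
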